7.2 Description of Statistical Methods

Continuous numeric variables will report as means with SD and compared using the Student’s t- or Wilcoxon rank-sum test. Categorical variables will be presented as counts and percentages and will be compared using the chi-square or Fisher’s exact test. To examine the effect of significant factors on two different groups (Group 1 vs Group 2) the hazard ratio of the interaction term will be calculated. To identify the independent predictors for in hospital NACE, 30day MACE and 30-day BARC bleedings, first univariate and then multivariate logistic regression models will apply. The BARC bleedings will be considered according to type of surgery. Specifically, BARC bleedings grade ≥ 3 will be considered in patients undergoing cardiac surgery, and BARC bleedings grade ≥ 4 will be taken into account for non-cardiac surgery. Covariates for multivariable models will be selected on the basis of a backward stepwise algorithm in a Cox proportional hazards model. Additionally, to minimise group differences on confounding covariates between patients who will be managed with consensus document (group 1) and those who will be received local practice (group 2), a 1:2 propensity score matching would be used. Propensity scores will be calculated with logistic regression, with multiple imputation and backwards elimination with a significance level to stay of 0.05. To ensure that the comparison between two groups (group 1 vs group 2) would not be bias, the proportion of patients who will not received consensus document within center that traditionally used it, will be excluded. The results will be presented as ORs with 95% confidence intervals (CI) and p values. For all

analyses, a two-sided $P <0.05$ will be required for statistical significance. All data will be analyzed using the Statistical Package of Social Sciences version 20 (IBM SPSS, Chicago, IL).

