action and they do not target the P2Y12 receptor. In addition, since they are renally cleared, dose adjustments are required among patients with impaired renal function. There are no randomized trials on bridging with small molecule GPIs and data derive from observational studies. Infusion should be commenced three days prior to surgical intervention, whereas clopidogrel and ticagrelor should be discontinued five days prior to surgery and seven days with prasugrel. GPI infusion should be interrupted at least four hours prior to surgery (eight hours in patients with creatinine clearance <30 ml/min).

P2Y12 inhibitors resumed within 24-48 hours after the intervention after confirmation of successful hemostasis, and with a loading dose. In patients with an increased bleeding risk in the post-operative period, clopidogrel should be preferred over prasugrel or ticagrelor. If gastrointestinal function has not yet recovered (e.g., abdominal surgery), intravenous infusion of antiplatelet agents (cangrelor or GPI) should be restarted after the surgical procedure, after careful evaluation of the bleeding risk. After complete intestinal recanalization, therapy with P2Y12 inhibitors should be resumed with a loading dose, after which the infusion of intravenous antiplatelet agents can be stopped. Because thrombotic complications occur most frequently soon after surgery, close post-operative clinical and electrocardiographic monitoring is strongly encouraged.

Notably, the impact of the application of the SAS 2 document on perioperative antiplatelet therapy in clinical practice has not been evaluated.

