4.2 Primary endpoint

- Rate of discontinuation of P2Y12 inhibitors and/or aspirin (without bridging) in the first 3 months after PCI with low risk characteristics and 6 months after PCI with high risk characteristics or any antiplatelet therapy discontinuation without bridging therapy

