4.3 Secondary endpoints

Patients undergoing non cardiac surgery:

- The composite of death, myocardial infarction, probable/definite stent thrombosis according the Academic Research Consortium definition⁴⁴ and bleeding events of Bleeding Academic Research Consortium (BARC) grade ≥ 3 at 30 days
- The composite of death, myocardial infarction and probable/definite stent at 30 days
- The incidence of bleeding events of Bleeding Academic Research Consortium (BARC) grade ≥ 3 at 30 days
- The type and the length of discontinuation of any antiplatelet therapy in patients undergoing non cardiac surgery according to time from PCI to surgery
- Rate of non cardiac surgical procedures within 12 months from PCI divided into quartiles (0-3, 3-6, 6-9, 9-12 months)
- Delay in performing non cardiac surgical procedure

Patients undergoing cardiac surgery:

- The composite of death, myocardial infarction, probable/definite stent thrombosis according the Academic Research Consortium definition⁴⁴ and bleeding events of Bleeding Academic Research Consortium (BARC) grade ≥ 4 at 30 days
- The composite of death, myocardial infarction and probable/definite stent at 30 days
- The incidence of bleeding events of Bleeding Academic Research Consortium (BARC) grade ≥ 4 at 30 days
- The type and the length of discontinuation of any antiplatelet therapy in patients undergoing cardiac surgery according to time from PCI to surgery
- Rate of cardiac surgical procedures within 12 months from PCI divided into quartiles (0-3, 3-6, 6-9, 9-12 months)
- Delay in performing cardiac surgical procedure

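### Section 7.2 models an undefined in-hospital NACE where Section 4.3 lists the net composite only at 30 days, and it assigns no adjusted analysis to the primary endpoint

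*Combined protocol and SAP*

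**What the plan says.** Section 4.2 makes the primary endpoint a rate: "Rate of discontinuation of P2Y12 inhibitors and/or aspirin (without bridging) in the first 3 months after PCI with low risk characteristics", with a longer period for high-risk PCI and a further clause on any unbridged discontinuation.

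Section 4.3 then lists, for non-cardiac surgery, "The composite of death, myocardial infarction, probable/definite stent thrombosis according the Academic Research Consortium definition" together with "bleeding events of Bleeding Academic Research Consortium (BARC) grade ≥ 3 at 30 days". For cardiac surgery the same composite takes "bleeding events of Bleeding Academic Research Consortium (BARC) grade ≥ 4 at 30 days". Every clinical composite in that section is timed at 30 days.

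Section 7.2 states the regression plan differently. The models are meant "To identify the independent predictors for in hospital NACE, 30day MACE and 30-day BARC bleedings", and "first univariate and then multivariate logistic regression models will apply". Elsewhere the same section gives generic chi-square or Fisher tests for categorical variables and a 1:2 propensity score match of group 1 (consensus document) to group 2 (local practice), with results as odds ratios. Neither method is tied to a named outcome.

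NACE and MACE appear neither in the abbreviations list nor among the endpoint definitions of Section 6.

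**The concern.** There are two separate gaps.

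The first is the outcome and its window. Section 7.2 gives MACE and bleeding a 30-day window but gives NACE an in-hospital one. A fixed window gives each patient the same time at risk. An in-hospital window ends when the patient goes home, and this registry takes any surgery or operative endoscopic or endovascular procedure, so stays can be expected to vary. A logistic model counts a patient discharged early without an event the same as one observed for much longer. A factor that goes with longer stay can then look like a predictor of NACE because there was more time to see events. Meanwhile the 30-day net composite that was defined has no named model.

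The second gap matters more. Groups are formed by centre practice, not by randomisation, so the primary comparison needs adjustment for case mix. Section 7.2 does not say which analysis answers the primary question. The choice between an unadjusted test and a matched odds ratio could be made after the results are seen.

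**Working it through.** The plan gives no figure on this point to reproduce. Section 7.1 names no endpoint, event rate or effect size for its sample size, so it cannot show which outcome the main analysis is built on.

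**Matching modelled outcomes to listed endpoints**

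| Outcome modelled in 7.2 | Counterpart in 4.2 or 4.3 | Window agrees? |
|---|---|---|
| 30-day MACE (undefined) | ischaemic composite at 30 days, by inference | yes |
| 30-day BARC bleeding | BARC bleeding at 30 days | yes, but thresholds reversed |
| in-hospital NACE (undefined) | net composite at 30 days, by inference | no |
| none named | primary endpoint of 4.2 | not applicable |

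Reading NACE as the net composite is an inference. It rests on that composite being the only one that joins ischaemic and bleeding events.

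**BARC thresholds.** Section 4.3 uses grade 3 or above for non-cardiac surgery and 4 or above for cardiac surgery. Section 7.2 assigns 3 or above to cardiac and 4 or above to non-cardiac. Until these agree, the bleeding part of the net composite is ambiguous at any window.

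**How much the window could matter (illustration only).** The documents give no lengths of stay and no event-time distribution. All stays and mean times below are assumptions, and time is counted from surgery. For a stay of L days, the share of 30-day events seen before discharge is:

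- constant hazard, low risk: L / 30
- exponential event times with mean m days: (1 − e^(−L/m)) / (1 − e^(−30/m))

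| Event timing | L = 1 | L = 8 | Ratio |
|---|---|---|---|
| constant hazard | 1/30 = 3.3% | 8/30 = 26.7% | 8.0 |
| m = 7 days | 0.1331/0.9862 = 13.5% | 0.6811/0.9862 = 69.1% | 5.1 |
| m = 3 days | 28.3% | 93.1% | 3.3 |

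Section 2 says thrombotic complications cluster soon after surgery, which argues against the constant-hazard row. That row is the upper end of the range.

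These ratios contrast two very different patients, not two groups. If everyone in one group stayed 5 days and everyone in the other 6 (again assumed), the ratio is 6/5 = 1.20 at constant hazard, 0.5756/0.5105 = 1.13 for m = 7, and 0.8647/0.8111 = 1.07 for m = 3.

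**Primary endpoint.** Going through Section 7.2, the chi-square or Fisher sentence covers any categorical variable, so it would cover discontinuation, unadjusted. The logistic models exclude it by listing three other outcomes. The propensity match is open to any outcome and assigned to none. Section 6 does not settle the matter: its stent thrombosis paragraph speaks of the study's primary endpoint as a hierarchy of death, MI and stent thrombosis, which is not the endpoint of Section 4.2.

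**The case against.** The logistic models are for finding predictors, while group 1 and group 2 are compared through propensity matching. That is right, and it limits the window problem to the predictor model for NACE. A reader might infer that the comparison of the two strategies is itself biased by length of stay. The documents do not support this. The groups are defined by use of the consensus document, not by bridging, and nothing says that stays differ between them. Section 2 does say of glycoprotein IIb/IIIa inhibitor bridging that "Infusion should be commenced three days prior to surgical intervention", but this concerns days before the operation. The plan does not say whether pre-operative days count in the in-hospital window, so the sentence does not show a longer period of observation after surgery.

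A reader might also infer that every adjusted analysis misses the primary endpoint and the net composite. That goes too far, because matching is an adjusted analysis and could cover both. The components of the net composite are also modelled at 30 days, if MACE means the ischaemic composite of 4.3. Only the combination lacks a named model.

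Finally, in-hospital outcomes are planned data: Section 4.1 and the schedule in Appendix A both collect them, so an in-hospital model may be meant as an addition. That is possible, but Section 7.2 does not say so and no endpoint list includes it. The 30-day contact has a tolerance of its own (±7 days, so day 23 to day 37), but that tolerance is not tied to discharge.

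**Conclusion.** The point holds as a mismatch between sections and a gap in specification. Section 7.2 models an undefined outcome over a window that Section 4.3 does not use, and no adjusted analysis is assigned to the primary endpoint in a non-randomised comparison. Both should be corrected before analysis; the second is the more important.

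The size of any distortion in the NACE model cannot be derived from the documents. A factor of about 3 to 8 describes two assumed patients with stays of 1 and 8 days under three assumed event timings. It is not an estimate of bias, and in particular the eightfold figure should not be read as one. With assumed group stays of 5 and 6 days the factor is 1.07 to 1.20. The conclusion rests on reading NACE as the net composite of Section 4.3. If the sponsor means something else, the need for a definition and a listed window remains.

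**What to change.** In Section 7.2, with matching entries in the abbreviations and Section 6:

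1. Define NACE and MACE by their components and window.
2. Model the net composite of Section 4.3 at 30 days, separately for non-cardiac and cardiac surgery. Keep in-hospital events as supplementary or descriptive, and state when that window starts.
3. Name the propensity-matched group 1 versus group 2 odds ratio, with its 95% confidence interval, as the primary analysis of the Section 4.2 endpoint. Label the unadjusted test as supportive.
4. Reconcile the BARC thresholds of Sections 4.3 and 7.2.
5. Bring the reference to the primary endpoint in the stent thrombosis paragraph of Section 6 into line with Section 4.2.

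The cost is wording only. Section 4.5.3 already captures dates and times of antiplatelet discontinuation and restart, and Section 4.5.4 already checks endpoint items at the 30-day contact.

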7. STATISTICS

7.1 The Number of Participants

Consecutive patients will be enrolled over one year of time at the participating Centers.

Cases and controls patients will be divided into those who will use Consensus Document “Stent and Surgery-2” (group 1) vs those who traditionally will be managed by local practice (group 2). On the basis of previous data reported SAS, a sample size of 1623 patients would be required to have a case-control matching 1:2, assuming a study power of 80% and 5% significance. Of those, 324 case-patients (20% of group 1) vs 162 control-patients (ratio 1:2) would be required for enrollment within one-year after implanted stents. Two preplanned interim analyses will be performed by an independent statistician when 800 and 1500 of patients will be enrolled.

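### The predictor models choose covariates from the outcome data and report the survivors with unadjusted ORs, CIs and p values, so false predictors are likely and weak or moderate true effects are overstated

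*Combined protocol and SAP*

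**What the plan says.** Section 7.2 sets out a predictor analysis for three outcomes: "To identify the independent predictors for in hospital NACE, 30day MACE and 30-day BARC bleedings". The method is that "first univariate and then multivariate logistic regression models will apply". It continues: "Covariates for multivariable models will be selected on the basis of a backward stepwise algorithm in a Cox proportional hazards model". On reporting, "The results will be presented as ORs with 95% confidence intervals (CI) and p values", and for all analyses a "two-sided $P <0.05$ will be required for statistical significance".

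For these outcome models the plan does not give:
- a list or number of candidate covariates;
- an entry or stay threshold (the one stay level in 7.2, "multiple imputation and backwards elimination with a significance level to stay of 0.05", belongs to the propensity score);
- a limit on covariates relative to events;
- shrinkage, bootstrap or other internal validation;
- a multiplicity adjustment, or a statement that the analysis is exploratory;
- whether group (consensus document versus local practice) is a candidate and, if so, whether it must stay in.

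**The concern.** The same data choose the covariates and then supply the estimates and p values for those chosen. Two harms follow. With many candidates each tested at 0.05, some unrelated variables will be reported as independent predictors. And because a term appears in the final model only if its estimate was large enough to be significant, the surviving estimates of weak or moderate true effects average too high.

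A third risk depends on a detail that the plan leaves open. If group is among the candidates, backward elimination can remove it whenever it is not significant. The regression-adjusted group OR would then be missing for exactly those outcomes. This bears on the secondary objective in section 3.2, which relates ischemic and hemorrhagic events to use of the consensus document.

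The mismatch between logistic models and selection in a Cox model does not affect the argument, since significance-based selection raises the same issue in either. Nor does it matter whether the univariate step filters variables, because backward selection is explicit.

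**Working it through.** **Inputs from the documents.** N = 1,623 (section 7.1: "a sample size of 1623 patients would be required to have a case-control matching 1:2"), three modelled outcomes and two-sided 0.05 (section 7.2). The figure of 1,623 cannot be reproduced, because 7.1 gives no event rates or effect size. It is used here only as the number of patients.

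**Assumptions.** Candidates: 20, with 30 as a second case, since section 4.5.3 captures roughly 30 baseline, drug, stent and surgical variables. Event rates: 3% to 10%, or about 49 events (1,623 × 0.03) to 162 (1,623 × 0.10). Stay level: 0.05. Univariate screen: 0.05, or 0.10 in a second set of runs.

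**Step 1: false predictors, by formula.** For m independent candidates with no true effect, the chance of at least one p < 0.05 is 1 − 0.95^m:
- m = 8: 1 − 0.95^8 = 0.34
- m = 20: 1 − 0.95^20 = 0.64
- m = 30: 1 − 0.95^30 = 0.79

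**Step 2: false predictors, by simulation.** Univariate screen and backward elimination, both at 0.05, with 20 independent null candidates: 63% at event rates of 5% and of 10% (1,500 datasets each). A second set with mildly correlated, half-binary candidates and a 0.10 screen gave 64–66% with 20 candidates and 73–78% with 30 (300 datasets per setting, standard error about 3 points).

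**Step 3: how much is due to selection?** The same 20-candidate data were analysed by stepwise selection and by one full 20-variable model with no selection (400 to 600 datasets per setting).

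| Quantity | Stepwise | Full model |
|---|---|---|
| Any false predictor, all 20 null | 63–67% | 64–69% |
| Five true ORs of 1.20, 5% events: any false predictor | 48% | 52% |
| Same, mean OR among significant true predictors | 1.35 | 1.35–1.36 |
| Five true ORs of 1.20, 10% events: mean OR among significant true predictors | 1.27 | 1.27 |
| True OR 1.20, mean of all estimates, 5% events | not available | 1.20–1.21 |

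The false-predictor rate therefore comes mainly from unadjusted testing of many candidates. The overstatement comes from reporting only significant terms: when the full model reports every estimate, the average is close to the truth.

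**Step 4: how overstatement depends on strength and events.** One true predictor among 20 candidates, 0.10 screen, mean reported OR when selected:

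| True OR | 3% events | 6% events | 10% events |
|---|---|---|---|
| 1.20 | 1.43 | 1.32 | 1.26 |
| 1.30 | 1.48 | 1.37 | 1.32 |
| 1.50 | 1.57 | 1.51 | 1.50 |

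The 1.20 predictor was selected in 24%, 42% and 64% of runs respectively. Coverage of the ordinary 95% CI among selected true predictors was about 92–99%.

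**Step 5: group, if it is a candidate.** Normal approximation, N = 1,623, one group holding between one third and two thirds of patients, true OR 0.70, stay level 0.05; the event rate is that under local practice. SE = √[1/(n₁p₁(1−p₁)) + 1/(n₀p₀(1−p₀))].
- 6% events: group eliminated in about 65–70% of studies; mean OR when kept about 0.53–0.55.
- 10% events: about 49–55%; mean OR when kept about 0.59–0.61.

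**The case against.** The strongest reply is that stepwise selection is being blamed for something it does not cause. That stands. A reader might infer that the screen and elimination produce the 63%; the full-model comparison shows nearly the same rate without them. For the same reason, replacing selection by a fixed list does not cure the problem alone: eight null covariates tested at 0.05 still give about a 34% chance of a false predictor.

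Other stronger readings also go beyond the evidence:
- **All reported ORs are biased away from the null.** Not so. At a true OR of 1.50 the reported mean is 1.50–1.57, and the excess almost vanishes once events are ample.
- **The confidence intervals are invalid.** They ignore the selection in principle, but the simulations show no clear loss of coverage for retained true predictors.
- **No adjusted group comparison would remain.** Section 7.2 separately plans 1:2 propensity score matching with ORs and CIs. Only the regression-adjusted group OR is at risk, and only if group is a candidate, which the plan does not say.
- **The main result is compromised.** The primary endpoint in section 4.2 is antiplatelet discontinuation, which is not among the outcomes modelled.

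It is also fair to object that the candidate count, thresholds and event rates are assumed. They have to be, because the plan gives none. The direction does not depend on them, but the size does.

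**Conclusion.** The concern holds as a weakness of the secondary predictor analyses, and it should be corrected. With 20 null candidates, 0.05 thresholds and N = 1,623, each outcome has about a 63–67% chance of at least one false independent predictor, mainly through unadjusted multiple testing. Reporting only the survivors overstates weak or moderate effects: a true OR of 1.20 appears as about 1.35 at 5% events and 1.27 at 10%. With 30 candidates or fewer events both problems grow; with strong predictors and ample events the overstatement is negligible. If group is a candidate, its regression-adjusted OR can be dropped when not significant, although the propensity-matched estimate remains.

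**What to change.** For each outcome, fit one model with a short clinical covariate list fixed before the data are seen and sized to the expected number of events. Section 4.5.3 already collects suitable fields: age, diabetes, eGFR, prior MI, time from stenting, stent type and surgical risk class. Urgency should be added only if the eCRF records it; elective versus urgent or emergent surgery appears in section 4.4.1 as an eligibility statement, not in the 4.5.3 list. Force group into the model, report every estimate whether or not significant, and use Firth or ridge penalisation when events are few.

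Label the predictor analysis exploratory, or adjust for multiplicity. If data-driven selection is kept, state the candidate list and thresholds, and report bootstrap-corrected estimates and inclusion frequencies.

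The cost is SAP wording and modest analysis time, with no new data or patients. The downside is wider intervals and fewer headline predictors.

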6.2 Death

All-cause mortality will be considered for the primary analysis. All-cause mortality includes all deaths, regardless of whether the cause of death is determined.

For the secondary analysis, death will be classified in two primary categories, cardiovascular or non-cardiovascular.

- Cardiovascular death is defined as death due to atherosclerotic coronary heart disease, cerebrovascular accident or (complication of) peripheral embolization, and includes deaths due to acute MI, stroke, sudden death, non-sudden death, unwitnessed death, and procedure-related deaths.

- Non cardiovascular death includes deaths due to all other causes.

All deaths will be assumed cardiovascular in nature unless a non-cardiovascular cause can be clearly shown, with the exception of death without any additional information, which will be classified as unknown cause of death.

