6.4 Bleeding Classification

All bleeding events will be considered in patients undergoing cardiac and non cardiac surgery.

Bleeding events will be classified according to BARC classification.

Bleeding Academic Research Consortium Definition for Bleeding (Ref 43)

- Type 0: no bleeding
- Type 1: bleeding that is not actionable and does not cause the patient to seek unscheduled performance of studies, hospitalization, or treatment by a healthcare professional; may include episodes leading to self-discontinuation of medical therapy by the patient without consulting a healthcare professional

- Type 2: any overt, actionable sign of hemorrhage (eg, more bleeding than would be expected for a clinical circumstance, including bleeding found by imaging alone) that does not fit the criteria for type 3, 4, or 5 but does meet at least one of the following criteria: (1) requiring nonsurgical, medical intervention by a healthcare professional, (2) leading to hospitalization or increased level of care, or (3) prompting evaluation

- Type 3

Type 3a: overt bleeding plus hemoglobin drop of 3 to <5 g/dL* (provided hemoglobin drop is related to bleed); any transfusion with overt bleeding

Type 3b: overt bleeding plus hemoglobin drop ≥ 5 g/dL* (provided haemoglobin drop is related to bleed); cardiac tamponade; bleeding requiring surgical intervention for control (excluding dental/nasal/skin/hemorrhoid); bleeding requiring intravenous vasoactive agents

Type 3c: intracranial hemorrhage (does not include microbleeds or hemorrhagic transformation, does include intraspinal); subcategories confirmed by autopsy or imaging or lumbar puncture; intraocular bleed compromising vision

- Type 4: CABG-related bleeding, including perioperative intracranial bleeding within 48 h, reoperation after closure of sternotomy for the purpose of controlling bleeding, transfusion of >5 U whole blood or packed red blood cells within a 48-h period, chest tube output >2L within a 24-h period
- Type 5: fatal bleeding

Type 5a: Probable fatal bleeding; no autopsy or imaging confirmation but clinically suspicious

Type 5b: Definite fatal bleeding; overt bleeding or autopsy or imaging confirmation

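### Section 7.2 reverses the BARC bleeding thresholds of Section 4.3, so that in non-cardiac surgery essentially only fatal bleeding would count.

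*Combined protocol and SAP*

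**What the plan says.** Section 4.3 lists the secondary endpoints separately for the two kinds of surgery. For non-cardiac surgery the bleeding endpoint is "The incidence of bleeding events of Bleeding Academic Research Consortium (BARC) grade ≥ 3 at 30 days". For cardiac surgery it is "The incidence of bleeding events of Bleeding Academic Research Consortium (BARC) grade ≥ 4 at 30 days". The same two thresholds appear in the composites with death, myocardial infarction and stent thrombosis, so Section 4.3 states its rule four times, consistently.

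Section 7.2 names in-hospital NACE, 30-day MACE and 30-day BARC bleeding as the outcomes of the regression models, and then fixes the bleeding threshold by type of surgery: "BARC bleedings grade ≥ 3 will be considered in patients undergoing cardiac surgery", while "BARC bleedings grade ≥ 4 will be taken into account for non-cardiac surgery".

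Section 6.4 gives the BARC list and sets no threshold by type of surgery. Two entries matter most here: "Type 4: CABG-related bleeding, including perioperative intracranial bleeding within 48 h" and "Type 5: fatal bleeding".

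**The concern.** The two sections give opposite definitions of the same endpoint in both surgical strata, and nothing in the documents reconciles them. Section 7.2 is the only place that says how bleeding is to be coded for the models, so a statistician who follows it would analyse a different variable from the one Section 4.3 defines.

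The consequence is not symmetrical. Type 4 belongs to CABG, so a threshold of grade 4 or higher in non-cardiac surgery drops every non-fatal bleed: those graded on haemoglobin drop, transfusion, surgical control or intracranial site. In cardiac surgery the lower threshold brings in type 3 bleeds that Section 4.3 leaves out. Haemorrhagic events are a stated secondary objective (Section 3.2), and the rationale in Section 2 is the balance between ischaemia and bleeding. Under Section 7.2 the bleeding side of that balance would almost vanish in non-cardiac patients.

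There is also a timing risk. Section 7.1 plans interim analyses at 800 and 1500 patients. If the conflict is noticed only then, someone will choose a definition with data in hand.

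**Working it through.** **Inputs**
- Thresholds as defined: Section 4.3.
- Thresholds as analysed: Section 7.2.
- BARC types: Section 6.4. Types 3a, 3b and 3c are non-fatal major bleeding, starting at "Type 3a: overt bleeding plus hemoglobin drop of 3 to <5 g/dL" or a transfusion accompanying overt bleeding. Type 4 is CABG-related. Types 5a and 5b are fatal.
- Death: Section 6.2, where "All-cause mortality includes all deaths, regardless of whether the cause of death is determined".

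**Step 1. Which types count under each rule**

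| Stratum | Section 4.3 | Section 7.2 |
|---|---|---|
| Non-cardiac | ≥3: 3a, 3b, 3c, 5a, 5b | ≥4: 5a, 5b |
| Cardiac | ≥4: 4, 5a, 5b | ≥3: 3a, 3b, 3c, 4, 5a, 5b |

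Type 4 is left out of the non-cardiac row because Section 6.4 ties it to CABG. The one exception would be a non-cardiac patient who also has CABG within the 30 days.

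**Step 2. Effect on the non-cardiac composite**

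The Section 4.3 composite is death, myocardial infarction, stent thrombosis or bleeding. If bleeding means only 5a and 5b, every such event is already an all-cause death. The bleeding component then adds no patient, and the composite equals death, myocardial infarction or stent thrombosis, which Section 4.3 already lists as a separate endpoint.

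**Step 3. Illustration of the loss of events**

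The documents give no bleeding rates and no split between cardiac and non-cardiac surgery. Assume 1,400 non-cardiac patients, 5–10% with BARC grade 3 or higher, and 0.2–0.5% with fatal bleeding. Events = patients × rate:
- Grade 3 or higher: 1,400 × 0.05 = 70, to 1,400 × 0.10 = 140.
- Fatal only: 1,400 × 0.002 = 2.8, to 1,400 × 0.005 = 7.

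**Step 4. Illustration of the loss of power**

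Take the planned 1623 patients split 1:2 (1623 / 3 = 541, and 2 × 541 = 1082), a two-sided 5% test and an assumed halving of risk. With d = |p1 − p2| and pooled rate p̄ = (541·p1 + 1082·p2) / 1623, the normal approximation is

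power = Φ[(d − 1.96·√(p̄(1 − p̄)(1/541 + 1/1082))) / √(p1(1 − p1)/541 + p2(1 − p2)/1082)].

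| Assumed rates | Power |
|---|---|
| 6% vs 3% | 80% |
| 2% vs 1% | 39% |
| 0.6% vs 0.3% | 17% |
| 0.2% vs 0.1% | 10% |

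The whole sample is used here, so the non-cardiac stratum alone would do worse. The 80% in the first row does not reproduce the plan's sample size: Section 7.1 states neither event rates nor an effect size, so its figure of 1623 cannot be rebuilt.

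**The case against.** The contradiction is not in dispute. The case on the other side concerns how far it reaches.

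- **The endpoints are secondary.** The primary endpoint is discontinuation of antiplatelet therapy, and the sample size is not tied to bleeding. This stands, and it limits the damage.
- **It looks like a transposition that can be undone.** Section 6.4 has all bleeds classified by BARC type, so either threshold can be applied later and no data are lost. This also stands. It makes the repair cheap, but it does not make the present sentence harmless, because that sentence governs the analysis.
- **The sentence may apply only to the predictor models.** It follows directly on the sentence about independent predictors. That reading is possible. Even so, the predictor models would use an outcome other than the defined endpoint, and the sentence that introduces the rule is worded generally.
- **NACE is never defined.** Section 7.2 takes NACE in hospital, while the composite in Section 4.3 is at 30 days. Carrying the error into NACE is therefore an inference. The stand-alone 30-day bleeding analysis is affected without it.
- **Other information on bleeding remains.** Section 4.5.3 also captures major bleeding, transfusions and reoperation for bleeding. The ischaemia–bleeding balance would thus be badly distorted rather than wholly unreadable. The same data items support Section 4.3, since transfusion, reoperation and the haemoglobin nadir are what type 3 grading needs.
- **Section 4.3 has a gap of its own.** Read literally, grade 4 or higher leaves only fatal bleeding in cardiac surgery other than CABG. This is a fair point, but a separate one, and it does not rescue Section 7.2.

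**Conclusion.** The concern holds. Section 7.2 reverses the thresholds of Section 4.3 in both strata, and Section 7.2 is the side that fits the plan's own BARC list badly. In non-cardiac surgery the counted types shrink from five to two, leaving essentially fatal bleeding alone; in cardiac surgery three non-fatal types are added. These statements follow from the text and need no assumption beyond reading type 4 as Section 6.4 defines it.

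The fall from 70–140 events to about 3–7, and the power figures, rest on assumed rates and an assumed number of non-cardiac patients; they show only the order of the loss. The effect on NACE depends on NACE meaning the Section 4.3 composite. The primary endpoint is unaffected. The sentence must still be corrected before analysis, because following it as written would analyse the wrong bleeding variable.

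**What to change.** Correct the sentence in Section 7.2 to agree with Section 4.3: BARC grade 3 or higher in non-cardiac surgery and grade 4 or higher in cardiac surgery, both for bleeding alone and wherever bleeding enters a composite. Do this before the first interim analysis, so that the definition is not chosen after data have been seen.

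The same edit could usefully define NACE and its time window, and say how type 4 applies to cardiac surgery other than CABG. These are clarifications and not conditions for the correction.

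The cost is one sentence. No new data are needed, and no figure in the documents changes.
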